1. Test the effectiveness of PfR in modifying key outcomes on parent-child relationships and relationships between partners which underlie violence against children and girls/women. The trial will be powered to detect meaningful change in four primary outcomes: parent-reported and child-reported harsh parenting and partner conflict. Secondary outcomes include positive parenting, parental support for children's education, child behaviour problems, parent/child mental health problems, material provision for children (all parent- and child-report), as well as inequitable gendered socialisation and parenting self-efficacy, including protecting children from sexual abuse (parent-report only).
2. Examine the cost effectiveness of PfR using incremental cost-effectiveness analyses (CEA) based both on the primary outcomes of harsh parenting and partner conflict as well as on disability-adjusted life years (DALYs);
3. Examine how three implementation variables – rural vs peri-urban locality, previously established groups vs new groups, and professional vs non-professional facilitators – affect participation, programme fidelity, and quality of delivery (measured quantitatively);
4. Examine the impact of implementation variables – participant engagement and quality of delivery by facilitators – on primary outcomes of parent- and child-report of harsh parenting and partner conflict. We will also examine associations between baseline characteristics and participant engagement to further understand potential barriers to participation and whether there are particularly vulnerable families that have greater challenges in attending the programme.
5. Qualitatively investigate five elements of implementation: (i) what training facilitators need (length, follow-up, who delivers training, location, etc.); (ii) what supervision facilitators need (frequency, by whom, nature of feedback, etc.); (iii) targeting of PfR at the most vulnerable families and how this can be done; (iv) disseminating PfR's messages beyond those participating in group sessions to operate at a community, as well as individual, level; (v) differences between Wakiso and Amuru Districts in facilitative and hindering contextual factors. We will explore how these affect participation, programme fidelity, quality of delivery, participant response and community-wide impact.

Hypotheses

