Hypothesis 1: PfR will significantly reduce rates of child maltreatment at 3-months follow-up, as measured by parent and child-reports of the ICAST-Trial Scale, in comparison to a control group receiving a one-hour lecture on parenting and partner relationships.

Hypothesis 2: PfR will significantly reduce rates of partner conflict at 3-months follow-up, as measured by parent and child-reports of an adapted version of the Conflict Tactics Scale and WHO Coercion scale, in comparison to a control group receiving a one-hour lecture on parenting and partner relationships.

Hypothesis 3: PfR will have a significant effect on secondary outcomes associated to the risk violence against children and intimate partner violence at 3-months follow-up, including positive parenting,

parental support for children's education, child behaviour problems, parent/child mental health problems, and material provision for children (all parent- and child-report), as well as inequitable gendered socialisation and parenting self-efficacy, including protecting children from sexual abuse (parent-report), in comparison to a control group receiving a one-hour lecture on parenting and partner relationships.

Hypothesis 4: PfR will be cost-effective in terms of incremental cost-effectiveness analyses (CEA) based both on the primary outcomes of harsh parenting and partner conflict as well as on disability-adjusted life years (DALYs).

Hypothesis 5: We hypothesise that the following modalities of PfR delivery on implementation outcomes and cost (i.e., attendance, competent adherence, and cost-effectiveness):

A) Geographical location (urban vs peri-urban). We hypothesise that there will be no difference between urban and peri-urban delivery on implementation and cost outcomes. While families living in higher density areas may have more accessibility to other support services, rural families may be easier to recruit due to closer inter-family dynamics.

B) Group composition (existing vs new). We hypothesise that recruitment from existing community groups (e.g., microfinance savings groups) will have higher levels of implementation and more cost-effective than newly formed groups. Higher participation rates will, in turn, result in reductions VAWC (via indirect effects).

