Parents allocated to the control arm will receive a two-hour structured lecture called *Parenting in a Nutshell* on parenting and partner relationships. Three topics will be covered: 1) child development; 2) positive parenting; and 3) resolving partner conflicts. Facilitators delivering this lecture will have same/similar expertise with the facilitators engaged in PfR. Their training will consist of two-hour course on how to deliver the lecture.

15. Outcomes measurements

All outcomes of intervention effectiveness will be measured at baseline, 8-months post-baseline, and 12-months post-baseline. Demographic measures will only be measured at baseline. All measures will be translated into Luganda for Wakiso and Acholi for Amuru and back-translated to check the accuracy of the translation.

Primary outcomes

Child maltreatment - physical and emotional abuse: ISPCAN Child Abuse Screening Tool-Trial Parent (ICAST-TP) - Parent Report

Child maltreatment will be measured using an adapted version of the ISPCAN Child Abuse Screening Tool-Trial scale (17 items, ICAST-Trial) [26]. The original version of the ICAST-Trial was reduced from 19 items for caregivers and 27 items for adolescents to increase study feasibility due to the scale of the study. Respondents will report on the overall frequency of maltreatment during the past month as

well as for subscales on physical abuse (10 items; e.g., “In the past 4 weeks, how often did you discipline your child by spanking, slapping or hitting with your hand”) and emotional abuse (7 items; e.g., “In the past 4 weeks, how often did you say things to shame your child in front of other people?”). Each item ranges from 0 to more than 8 times and is summed to assess frequency of overall abuse as well as for each individual subscale.

[Time Frame: Baseline, 8-months post-baseline, and 12-months post-baseline]

Child maltreatment - physical and emotional abuse: ISPCAN Child Abuse Screening Tool-Trial Parent (ICAST-TC) - Child Report on Male Parent Figure

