Interviews and focus groups will occur during the post-evaluation and examine the following themes: 1) participants observed change in parenting practices and child behaviour at home during programme; 2) acceptability and appropriateness of programme materials, delivery, and key programme components; and 3) existing barriers to participation during sessions and engagement in home practice and other activities. Interviews will also explore facilitators’ challenges in implementing the programme on both a process (e.g., using a collaborative approach and/or explaining concepts such as child-led play) and logistical level (e.g., recruitment, session length, location, meals).

Cost effectiveness data collection

Programme costs will be calculated using a micro-costing approach, multiplying resource use by unit costs, divided into 1) start-up costs including costs required for coordinating recruitment, community mobilisation, and facilitator training; 2) programme delivery costs which includes staff-time, transportation, and other materials for home-based individual consultations, parent-group sessions, and supervision sessions; and 3) administrative costs to manage the implementation.

17. Blinding

The allocation status of other participating families will be concealed from participants, thus reducing the potential for contamination. Research assistants conducting data assessments and statisticians conducting analysis will be blind to allocation in order to minimise assessment bias [40, 41]. Different groups of research assistants will be employed for outcome assessments and monitoring of implementation fidelity and adherence. Any instances of compromised blinding will be immediately reported. In the case of instances of harm or severe abuse being reported by a participant at any stage of the study, the allocation status of the participant will be un-blinded. All cases of un-blinding will be reported. Because of facilitators’ involvement in the programme implementation, blinding will not be possible for service providers. Similarly, of course, participants cannot be blind to their own treatment condition.

18. Data collection, retention, and management

Data collection

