In accordance to the procedures followed in the pre-post pilot study, qualitative data analysis will explore participants' and facilitators' views and experience using a thematic analysis approach with open, axial, and selective coding [60]. Two independent raters will assess and code data from focus group and in-depth interview transcripts. The study will investigate emergent themes regarding 1) participants observed change in parenting practices and partner relationships during programme; 2) acceptability and appropriateness of programme materials, delivery, and key programme components; and 3) existing barriers to participation during sessions and engagement in home practice and other activities. Interviews will also explore facilitators' challenges in implementing the programme on both a process (e.g., using a collaborative approach and/or explaining concepts such as child-led play) and logistical level (e.g., recruitment, session length, location, meals). After consensus regarding the themes is reached within the research team, the assessors will re-examine the transcripts for evidence supporting these themes. These themes will then be grouped using axial coding into larger categories and analysed according to their properties. Finally, the categories will be integrated using selective coding into a larger theoretical representation of the shared experiences and perspectives [61].

Cost effectiveness analyses

Incremental cost effectiveness analyses (CEA) will be conducted from the payer's perspective (excluding participant costs) to assess whether the benefits of each component appear to be worth the added costs. Programme costs will be calculated using a micro-costing approach, multiplying resource use by unit costs. For outcome measures, in addition to assessing changes in the overall ICAS-Trial and partner conflict scores, the change in quality-adjusted life-years (QALYs) will be studied. Incremental cost effectiveness ratios (ICERs) will be calculated as the incremental change in costs divided by the incremental change in three health outcomes: the overall maltreatment, partner conflict, and QALYs. An ICER of \$50,000 or less per QALY gained is reasonably to be considered cost-effective. Bootstrapping techniques will be used to conduct uncertainty analyses to assess variability in our findings from potential sampling bias.

21. Data monitoring

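### The only cost-effectiveness rule is per QALY, but the trial measures no health-state utility, so the QALY result can only be modelled from outside weights and should be labelled and tested as such

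*Protocol*

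**What the plan says.** Section 20, Cost effectiveness analyses, names the ICAST-Trial and partner conflict scores as outcome measures and adds that "the change in quality-adjusted life-years (QALYs) will be studied". The ICERs divide incremental cost by the "incremental change in three health outcomes: the overall maltreatment, partner conflict, and QALYs". One decision rule follows: an ICER of $50,000 "or less per QALY gained is reasonably to be considered cost-effective". No threshold is given per unit of maltreatment or partner conflict, or per DALY. Bootstrapping is the only uncertainty method named, and its stated target is variability that comes from sampling.

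Section 15 says "All outcomes of intervention effectiveness will be measured at baseline, 8-months post-baseline, and 12-months post-baseline" and then lists the measures. Its paragraph on cost-effectiveness data collection reads "Programme costs will be calculated using a micro-costing approach, multiplying resource use by unit costs, divided into 1) start-up costs" and goes on to delivery and administrative costs. It describes nothing on the effect side.

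Section 7 uses a different health metric. Objective 2 bases the analysis on "harsh parenting and partner conflict as well as on disability-adjusted life years (DALYs". Hypothesis 4 says that "PfR will be cost-effective in terms of incremental cost-effectiveness analyses (CEA", and again names DALYs.

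**The concern.** A QALY is time weighted by a preference-based value for the health state lived in. To measure a QALY change within a trial, each participant needs an instrument whose answers convert to such a value at each visit. Section 20 places QALYs beside two measured scores as if they were the same kind of quantity, and attaches the sole decision rule to them.

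At stake is how the answer to Hypothesis 4 will be read. The only yardstick for calling the programme cost-effective is per QALY. If that quantity depends on weights brought in from elsewhere, and the reported interval reflects resampled trial data alone, readers will take a conditional, modelled verdict for a trial-measured one.

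**Working it through.** No plan figure needs reproducing. The check sets what Section 20 requires against what Section 15 collects, then follows the consequence algebraically.

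**1. Is there a utility instrument?** The candidates nearest to health status in Section 15 are:

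| Measure | Scoring described | Timing |
|---|---|---|
| Adult depression (DASS subscale) | Sum of items | Baseline, 8, 12 months |
| Parenting stress (PSS, 9 items) | Sum of items | Baseline, 8, 12 months |
| Child behaviour (CABI, parent and child report) | Sum of items | Baseline, 8, 12 months |
| Family stressors, including illness and child disability | Presence or absence, summed | Baseline only |
| Disability item in the demographics | Descriptive | Baseline only |

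None is described with preference weights or a value set, and the baseline-only items cannot show change. The other measures cover violence, coercion, attitudes, parenting, education, substance use, prosocial behaviour, gender roles, respectability, communication, COVID-19 impact, poverty, food security and process. Instruments yielding a utility: 0. Stated routes from a collected score to QALYs: 0. Thresholds: 1, per QALY.

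**2. What would a QALY ICER then be?** Take the simplest case, with ΔC the cost difference, Δs the randomised difference in a collected score (positive for improvement), and w an outside weight in QALYs per unit of score:

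ICER = ΔC / (Δs × w)

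The ICER is inversely proportional to w. With ΔC and Δs both positive, the rule is met when

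ΔC / (Δs × w) ≤ 50,000, that is, when w ≥ ΔC / (50,000 × Δs).

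On identical trial data the verdict can therefore change as w crosses that break-even value. A non-linear mapping, or one through the depression score, changes the algebra but not the dependence on an outside input.

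**3. What does the bootstrap cover?** If w is estimated independently of the trial, then to first order

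CV²(Δs × w) ≈ CV²(Δs) + CV²(w)

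where CV is the standard error divided by the estimate. Resampling trial data with w held fixed reproduces the first term only. Whatever CV(w) is, if it is above zero it is left out of the interval.

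**4. Does reconciling DALYs and QALYs remove the problem?** No. Disability weights are external by construction, so DALYs need no utility questionnaire, but the protocol states no weights and no conversion for DALYs either. The result would still be modelled.

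**The case against.** The strongest reply is that value sets, mapping functions and sensitivity analyses commonly belong in a statistical or health-economic analysis plan, which is not shown here. Section 20 says that QALY change will be studied; it does not say that utilities will be elicited from participants, so modelling them contradicts nothing. This stands in part. A missing mapping algorithm alone would be no finding. But an analysis plan can add a mapping and cannot add a questionnaire, and the protocol itself lists QALYs beside measured scores and ties its only rule to them.

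Three stronger readings are tempting, and the documents do not support them.

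- A reader might infer that no QALY or DALY result is possible. It is: depression, child behaviour and violence frequency are collected at all three visits and could be inputs to a model.
- A reader might infer that the ICER would reflect the outside assumption and not the randomised comparison. It would reflect both: Δs is still the between-arm difference, and the weight rescales it.
- A reader might want a fold-range for how far the ICER could move. The protocol gives no weights, so none can be derived from it.

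The bootstrap point is also conditional. The protocol does not rule out sensitivity analysis; it names none for this purpose.

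Finally, deleting the QALY ICER and its threshold would go too far. It would leave Hypothesis 4 with no criterion, since no value is set per unit of either score, and it would abandon part of Objective 2.

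**Conclusion.** The point holds in a limited form. A QALY change cannot be measured directly from the listed data; it can only be modelled from outside weights that the protocol does not identify. With bootstrapping as the only uncertainty method, the interval around the QALY ICER and the threshold verdict would look more certain than they are.

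The reach is one of three ICER denominators and the single decision rule. The ICERs per unit of maltreatment and of partner conflict rest on measured scores and are unaffected, as are the primary effectiveness analyses. The size of the understated uncertainty cannot be stated, because it depends on weights that the protocol does not give.

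This rests on two assumptions: that Section 15 is the full list of measures, and that no sensitivity analysis on the weights is planned elsewhere. If an analysis plan already contains one, what remains is to label the result as modelled in the protocol. The matter should be corrected, but it does not threaten the trial's main conclusions.

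**What to change.** In Section 20, under Cost effectiveness analyses:

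- Define the trial-based analysis as cost per unit reduction in the ICAST-Trial and partner conflict scores.
- Choose one health metric, QALY or DALY, and reconcile it with Objective 2 and Hypothesis 4 in Section 7. Label it a modelled secondary analysis, and name in advance the external weights and the collected scores to which they apply.
- Vary those weights in sensitivity analysis in addition to the bootstrap. Reporting the break-even weight shown above would be a compact way to do this.
- State that any verdict against the threshold is conditional on the weights.

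The cost is wording in Sections 7 and 20 and a little more analysis work, with no new data collection. The real concession is that the threshold verdict on Hypothesis 4 becomes a modelled conclusion and no longer a trial-measured one.

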C) Facilitator Experience (professional vs community). We hypothesise that although professional facilitators may achieve higher levels of implementation, community facilitators may be a more cost-effective approach and may also result in better implementation due to stronger buy-in at the community level. As a result, there will be no difference between components on VAWC (via indirect effects).

8. Trial design

We will use an effectiveness-implementation hybrid type 2 design to a) determine the effectiveness and cost-effectiveness of PfR, and b) determine the feasibility and impact of three different implementation strategies in terms of programme delivery.[21] We will conduct a cluster randomised controlled trial (cRCT) in a total of 54 clusters (1:1 intervention: control; 4 groups of 10 parents per cluster, 50% male 50% female, 2,160 in total or 1,080 adult participants per arm). In addition, approximately 1,080 children 10-14 years will be assessed ($N = 540$ per arm). We will also assess the quality of delivery of PfR in terms of competent adherence of 108 facilitators (1 per group, 4 per cluster).

We will also examine three different factors related to programme implementation within the clusters allocated to PfR (approximately 27 clusters, 40 parents per cluster): 1) geographical location (rural vs. peri-urban), 2) group composition (existing vs. newly formed groups), and 3) facilitator experience (experience vs. novice). Efforts will be made to have equal numbers of clusters receiving each type of component by testing every combination of implementation components in eight different experimental conditions ($N 3$ clusters and 120 families per condition).

Section 3: Methods

9. Study setting

The study will be conducted in two districts, Wakiso and Amuru, each of them contributing parental participants to both intervention and control arms. Participating clusters will either be villages or wards (i.e., groups of villages) depending on their population size and geographical proximity.

10. Eligibility criteria

Participants must have provided written, informed consent prior to the occurrence of any study procedures.

Inclusion criteria for participating parents or caregivers:

1. Age 18 or older;
2. Primary caregiver responsible for the care of a child between the ages of 10 and 14;
3. Agreement to participate in the PfR programme if allocated to the treatment condition;
4. Provision of consent to participate in the full study.

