For the evaluation of implementation components, we conducted similar sensitivity power analyses in order to calculate the minimum detectable Cohen's D effect size to obtain a significant effect of each component level on implementation outcomes of participation rates and implementation quality. Following recommendations for component selection by Collins et al. (2016) and Watkins et al. (2016), we assumed a Type 1 error of $p < 0.10$, and 80% power with a sample size of 480 adults and an ICC of

0.05. Thus, this sample size has sufficient power to detect significant component effects at Cohen's $d = .26$ on implementation outcomes (i.e., implementation fidelity, competent adherence, and participation).

14. Interventions

Intervention group – Parenting for Respectability

PfR was developed over five years following the Six Steps for Quality Intervention Development (6SQuID) model [22]. It initially underwent formative evaluation over two years (2014-2016) with six groups in three villages in Wakiso District [20]. *PfR* is a 16-session manualised programme starting with nine single sex sessions followed by seven mixed sex sessions, delivered once a week by two local facilitators who receive one week's training [23]. The programme draws on parents' pre-existing motivation to maintain respectability, largely achieved through children's good behaviour and respect for elders and builds on parents' existing skills and experience. Activities were developed specifically for PfR or adapted from other parenting programs, including *Project H*, *Stepping Stones*, *Mema kwa Jamii*, the *International Child Development Programme* and *Parenting for Lifelong Health* [24]. The programme addresses four familial processes associated with GBV and VAC: poor parental bonding and child attachment; harsh parenting; inequitable socialisation by gender and parental conflict. A particular goal is to involve fathers, whom most parenting programmes find hard to recruit, and the first nine sessions are delivered in single-sex groups. The intervention's rationale, program theory and formative evaluation are described elsewhere [25].

Control group - Lecture

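### The only cost-effectiveness threshold, $50,000 per QALY, has no stated source or link to Uganda and is in a different unit from Hypothesis 4, which names DALYs

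*Protocol*

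**What the plan says.** Section 20, under Cost effectiveness analyses, sets the perspective: "Incremental cost effectiveness analyses (CEA) will be conducted from the payer's perspective", with participants' own costs left out. ICERs are to be formed for "three health outcomes: the overall maltreatment, partner conflict, and QALYs". For the QALY ratio only, a value of $50,000 "or less per QALY gained is reasonably to be considered cost-effective". Bootstrapping is planned for the uncertainty analysis.

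The objectives use another unit. In Section 7, Objective 2 and Hypothesis 4 rest cost-effectiveness on harsh parenting and partner conflict "as well as on disability-adjusted life years (DALYs"). Neither mentions QALYs.

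On setting, Section 9 states: "The study will be conducted in two districts, Wakiso and Amuru". The background, just before Section 7, reports that government and non-governmental organisations are interested in scaling the programme up, and names the best route to scale-up as one of two open uncertainties.

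**The concern.** A cost-effectiveness threshold expresses what a particular payer is prepared to give up for a unit of health. The analysis is done for a payer, but that payer is never identified, and nothing connects $50,000 to anyone who might fund the programme in Uganda. The figure has no reference, although another benchmark in Section 20, the 80% fidelity standard, does have one.

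The unit adds a second problem. QALYs gained and DALYs averted are different measures, so a threshold per QALY does not by itself decide a hypothesis stated in DALYs.

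Cost-effectiveness is part of the overall goal in Section 7, alongside effectiveness. If the figure is applied as written, the trial could report the programme as cost-effective by a standard with no shown relevance to those who would pay for it. It could also report on Hypothesis 4 using a measure that the hypothesis does not name.

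**Working it through.** **Where the figure comes from.** The $50,000 is asserted, so there is no calculation to reproduce. No other part of the protocol supplies a source, currency year or country basis.

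**Measures and decision values, side by side.**

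| Measure | Objective 2 and Hypothesis 4 | ICER in Section 20 | Decision value |
|---|---|---|---|
| Harsh parenting / maltreatment | yes | yes | none |
| Partner conflict | yes | yes | none |
| DALYs | yes | no | none |
| QALYs | no | yes | $50,000 |

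The one measure with a decision value is the one that Hypothesis 4 does not name.

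**How permissive the figure is.** The protocol gives no programme cost, so the cost per parent, incremental to the lecture, is an assumption.

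Break-even QALY gain = incremental cost per parent / 50,000. Days of full health = gain × 365.

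| Assumed cost per parent | Break-even gain (QALY) | Days of full health |
|---|---|---|
| $100 | 100 / 50,000 = 0.002 | 0.7 |
| $200 | 200 / 50,000 = 0.004 | 1.5 |
| $300 | 300 / 50,000 = 0.006 | 2.2 |
| $500 | 500 / 50,000 = 0.010 | 3.7 |
| $1,000 | 1,000 / 50,000 = 0.020 | 7.3 |

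**Is $100 to $300 plausible for this delivery model?** Section 14 gives 16 sessions and Section 8 gives groups of 10 parents. Facilitators per group are one in Section 8 and two in Section 14. Facilitator-sessions per parent are therefore 16 × 1 / 10 = 1.6 or 16 × 2 / 10 = 3.2. At an assumed $100 per facilitator-session, all costs included, this comes to $160 to $320 per parent. The break-even gain is then 0.0032 to 0.0064 QALY (1.2 to 2.3 days). The $100 is not in the protocol. Section 15 (Cost effectiveness data collection) also counts start-up, supervision, home consultations and administration, so the true figure could be higher.

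**Break-even gain against sampling error.** Section 13 gives 960 adults per arm in 24 clusters, that is 40 per cluster, with ICC 0.05. The design effect is 1 + 39 × 0.05 = 2.95. For an assumed QALY SD of 0.1 to 0.2 (the protocol gives none), the SE of the arm difference is SD × √(2 × 2.95 / 960), or 0.008 to 0.016.

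Suppose the true gain is zero. By the normal approximation, the share of positive point estimates that would still meet the $50,000 rule is:

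| Assumed cost per parent | SD 0.1 | SD 0.2 |
|---|---|---|
| $100 | 80% | 90% |
| $200 | 61% | 80% |
| $500 | 20% | 52% |
| $1,000 | 1% | 20% |

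At an SD of 0.05 the shares are lower: 61% at $100 and 31% at $200.

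**The case against.** A reader might infer two stronger things, and the documents support neither.

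The first is that this rule decides Hypothesis 4 and makes a positive answer close to automatic. The rule is not stated for Hypothesis 4. It attaches to one of three ICERs, in a unit the hypothesis does not use. As written, Hypothesis 4 has no matching decision value, which is a different fault from having a lenient one.

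The second is that almost any small gain would pass. That depends on a cost, a QALY gain and an SD that the protocol does not give. Cost per parent cannot be set against $50,000 without a QALY gain. The inference is reasonable at roughly $100 to $300 per parent, weakens at $500 and is overstated near $1,000. A zero or negative gain fails at any positive incremental cost.

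Three further points can be made for the plan:

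- **The payer is open.** The background reports interest from government and non-governmental organisations but does not define the payer. The study is foundation-funded, and Section 25 lists funders and development partners among its audiences. This stands, and it is why the payer has to be named before a threshold is chosen.
- **Uncertainty is partly covered.** Bootstrapping is planned, and its display is commonly left to an analysis plan, which is not at hand. This stands as to display. It does not explain the threshold that the protocol has already fixed.
- **The wording is mild.** The sentence calls the figure a reasonable benchmark and does not label it a success criterion. Even so, it is the only benchmark given, and a reported conclusion would rest on it.

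**Conclusion.** The point holds in two parts that need no outside assumption. First, the protocol's only cost-effectiveness decision value has no source, price year or stated link to Uganda or to a defined payer. Second, it is expressed in QALYs while Objective 2 and Hypothesis 4 specify DALYs. Both are faults in what the protocol fixes; neither is a detail left for an analysis plan.

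The size of the leniency is conditional on assumed cost. At $100 to $300 per parent the rule is met by 0.002 to 0.006 QALY, about 0.7 to 2.2 days of full health. At $500 or more it needs at least 0.010 QALY. The documents offer no alternative threshold, so no multiple of a correct figure can be claimed. The fault should be corrected before analysis. It does not touch the effectiveness comparison.

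**What to change.** In Section 20, state who the payer is. Replace $50,000 with a threshold relevant to that payer in Uganda, giving its source, currency and price year, and fix it before analysis. A stated fraction of national income per head is one example only; the documents give no ground for preferring it.

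Use one health unit, DALY or QALY, in Objective 2, Hypothesis 4 and Section 20, and express the threshold in that unit.

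From the bootstrap already planned, report the probability that PfR is cost-effective across a range of thresholds, and base the Hypothesis 4 conclusion on that.

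The cost is one rewritten rule, consistent wording in three places and one extra output. No new data collection is needed for the threshold itself. The downside for the sponsor is that a verdict of cost-effective becomes harder to reach.
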